7.8.3 Vital signs

For vital signs (blood pressure and pulse rate), listings including change from baseline will be presented by planned time point based on the last value of the subject at that planned time point (or assigned to that planned time point).

Clinically relevant findings in vital signs will be reported as AEs.

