5.2.4 Electrocardiogram

5.2.4.1 12-lead resting ECG

Recording

Twelve-lead resting ECGs (I, II, III, aVR, aVL, aVF, V1 - V6) will be recorded using a computerised electrocardiograph at the time points given in the [Flow Chart](#). Precise electrode placement will be performed according to the method of [REDACTED] and [REDACTED], modified by [REDACTED] and [REDACTED], i.e. hips and shoulders instead of ankles and wrists. Precise electrode placement will be marked with an indelible mark on the skin to allow reproducible placement throughout the trial.

To achieve a stable heart rate at rest and to assure high quality recordings, the site personnel will be instructed to assure a relaxed and quiet environment so that all subjects are at complete rest.

All ECGs will be recorded for 10 s after subjects have rested for at least 5 min in a supine position. ECG recording will always precede all other trial procedures scheduled for the same time, except for blood drawing from an intravenous cannula that is already in place, to avoid compromising ECG quality.

ECGs will be recorded as single ECGs or as triplicate ECGs, i.e. three single ECGs recorded within 180 s, as indicated in the Flow Chart.

ECGs may be repeated for quality reasons due to, for instance, alternating current artefacts, muscle movements, or electrode dislocation. For repetition within triplicate ECGs, the time window of 180 s applies as well. The repeat ECGs are assigned to the respective scheduled time point.

Additional (unscheduled) ECGs may be collected by the investigator for safety reasons. These ECGs are assigned to the prior scheduled time point in the Sponsor's database.

Storage

All ECGs will be stored electronically in the System provided by [REDACTED].

Data transfer

All triplicate ECGs will be transferred electronically to the central ECG laboratory [REDACTED] for evaluation.

Proprietary confidential information © 2020 Boehringer Ingelheim International GmbH or one or more of its affiliated companies

In case of ECGs repeated due to quality reasons, only the repeated ECG recordings will be transferred to the central ECG lab, whereas the initially recorded ECGs will be discarded. Unscheduled ECGs, i.e. those taken for safety reasons, will be transferred to the central ECG lab, but will not be included into the statistical analysis of interval lengths.

Data transfer from the central ECG lab to the sponsor is described in a document that is filed in the TMF.

Evaluation

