4. CHANGES IN THE PLANNED ANALYSIS OF THE STUDY

The study was prematurely stopped after the first dose group (25mg BI 894416) due to a disadvantageous benefit risk ratio based on newly received data from another study with BI 894416.

Consequently, only a subset of the analyses planned in the CTP will be performed. Tables will be provided for disposition, demography, adverse events and standard safety analysis (including the primary endpoint) and for PK endpoints (including the secondary endpoints). For all study endpoints, listings will be provided. That means, for several variables, only listings will be provided and no descriptive analysis will be carried out. This applies to, for example, medical history, concomitant medication and non-drug procedures, laboratory data, vital signs and ECG.

As there is only one dose group available, no dose proportionality analysis will be done. Secondary endpoints (AUC_{0-∞} and C_{max} of BI 894416) will be analysed descriptively only.

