6.7 BASELINE, TIME WINDOWS AND CALCULATED VISITS

The baseline value is defined as the last measurement before trial medication administration.

Section 6.1 of the CTP: *Exact times of measurements outside the permitted time windows will be documented. The acceptable time windows for screening and the end of trial examination are provided in the CTP Flow Chart.*

Trial measurements and assessments scheduled to occur 'before' trial medication administration at Day 1 are to be performed and completed within a 2 h-period prior to the investigational medicinal product administration (including blank values for PK). A blank urine sample for PK will be collected within 3 h before drug administration.

The acceptable deviation from the scheduled time for vital signs and ECG will be ± 10 min for the first 4 h after investigational medicinal product administration and ± 30 min thereafter. For laboratory test, the acceptable deviation is ± 30 min.

(...)

The acceptable deviation from the scheduled time for neurological tests is ± 45 min on Day 1 and ± 90 min for other days.

Adherence to time windows will be checked via the consistency check listings at the RPM.

Unscheduled measurements of laboratory data and vital signs data will be assumed to be repeat measurements of the most recent scheduled measurement (e.g. for follow-up or confirmation of a particular value). Therefore, unscheduled measurements will be assigned to the planned time point of the previous scheduled measurement.

There will be a centralised evaluation of the 12-lead ECG recordings at the time points and for the ECG recordings specified in Table 6.7: 1 below:

Table 6.7: 1 Time schedule of 12-lead ECG recordings

Visit	Day	Planned time [hh:mm] (relative to drug administration)	Study phase	Central evaluation
1	-28 to -1		Screening	NA
2	-1	-24:00	Pre-dose	Three triplicate ECGs**
	1	-01:00	Baseline	Triplet ECG*
		00:30	On treatment	Triplet ECG*
		01:00	On treatment	Triplet ECG*
		01:30	On treatment	Triplet ECG*
		02:00	On treatment	Triplet ECG*
		02:30	On treatment	Triplet ECG*

		03:00	On treatment	TriPLICATE ECG*
		04:00	On treatment	TriPLICATE ECG*
		06:00	On treatment	TriPLICATE ECG*
		08:00	On treatment	TriPLICATE ECG*
		12:00	On treatment	TriPLICATE ECG*
	2	24:00	On treatment	TriPLICATE ECG*
		34:00	On treatment	NA
	3	48:00	On treatment	NA
	4	72:00	On treatment	NA
3	15 to 17		End of trial examination	NA

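### Does basing the vital-signs listing on the last value at each planned time hide abnormal readings behind their own repeats?

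*SAP*

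**What the plan says.** Three rules act together.

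- **Assignment (SAP 6.7).** "Unscheduled measurements of laboratory data and vital signs data will be assumed to be repeat measurements of the most recent scheduled measurement", the stated example being "for follow-up or confirmation of a particular value". As a result, "unscheduled measurements will be assigned to the planned time point of the previous scheduled measurement".
- **Selection (SAP 7.8.3).** The vital-signs listings, which include change from baseline, are "presented by planned time point based on the last value of the subject at that planned time point". A parenthesis extends this to values assigned to that time, so repeats are included on purpose.
- **Baseline (SAP 6.7).** "The baseline value is defined as the last measurement before trial medication administration". The last-value convention is thus used before dosing as well as after it.

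SAP 4 sets the scope after the stop: for several variables "only listings will be provided and no descriptive analysis will be carried out". It continues: "This applies to, for example, medical history, concomitant medication and non-drug procedures, laboratory data, vital signs and ECG". SAP 7 has the individual values of all subjects listed. SAP 7.8.3 sends clinically relevant vital-sign findings to adverse-event reporting.

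For ECG, Protocol 5.2.4.1 says that unscheduled safety recordings "will be transferred to the central ECG lab, but will not be included into the statistical analysis of interval lengths". The same section also assigns those recordings to the prior scheduled time in the sponsor's database.

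**The concern.** A repeat is often taken because the scheduled reading looked wrong. If the repeat then takes over that time point, the rule acts mainly on notable readings. It tends to exchange them for later values that lie closer to normal, partly through regression to the mean and partly because a short-lived effect has begun to fade. That is selection on the outcome, and a safety analysis should normally avoid it.

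The stakes seem higher here because the listing is the only planned quantitative view of blood pressure and pulse-rate change. Protocol 7.3.4 says vital signs will be assessed for on-treatment change from baseline, and an in-house single-dose trial exists partly to show transient effects. The ECG rule, which keeps unscheduled recordings out of the interval analysis, looks like the opposite policy with no reason given.

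**Working it through.** **1. What the rule can touch.** The documents give no vital-signs SD, no on-treatment repeat trigger and no figure for this rule, so there is nothing to reproduce. The planned outputs are:

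| Output | Uses the last-value rule? |
|---|---|
| Primary endpoint (subjects with drug-related AEs) | No |
| AE tables | No; they depend on the investigator's judgement of relevance |
| Summary of vital-sign change | Not produced (SAP 4) |
| Vital-signs listing, 8 subjects | Yes, for the computed difference |

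**2. Size in a simple model.** All inputs are assumptions: true systolic pressure 120 mmHg for everyone, measurement SD s = 6 to 10, a drug effect of +20 at the scheduled reading, a fraction f of it left at the repeat, and a repeat whenever the reading exceeds 140. The 140 limit is borrowed from exclusion criterion 2, which concerns eligibility. Since 120 + 20 = 140, half of the scheduled readings trigger a repeat. Then:

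- share of triggering readings whose repeat is at or below 140: Φ((20 − 20f)/s);
- average fall of a triggered entry: 20(1 − f) + 0.798s;
- shift averaged over all readings: half of that.

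| f | Repeat ≤ 140 | Fall of a triggered entry (mmHg) | Averaged shift (mmHg) |
|---|---|---|---|
| 0.50 | 84% to 95% | 14.8 to 18.0 | 7.4 to 9.0 |
| 0.79 | 66% to 76% | 9.0 to 12.2 | 4.5 to 6.1 |
| 0.89 | 59% to 64% | 7.0 to 10.2 | 3.5 to 5.1 |
| 1.00 | 50% | 4.8 to 8.0 | 2.4 to 4.0 |

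**3. Which f is credible.** An unscheduled value goes to the most recent scheduled reading, so its delay cannot exceed the gap to the next one. The Flow Chart's columns are shifted in the text, but vital signs appear to be taken at gaps of 15 to 60 min from 0:30 to 4:00. Protocol 6.1's tighter ±10 min window over the first 4 h fits that. Protocol 1.2.2 gives a half-life of 2.96 to 5.31 h. If effect follows concentration and the shorter half-life applies, the fraction left is 2^(−0.5/2.96) = 0.89 after 30 min and 2^(−1/2.96) = 0.79 after 60 min. A halved effect (f = 0.50) needs a delay of about 3 h, which the schedule rules out in this window.

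**4. Letting subjects differ.** The simple model makes all variance independent between reading and repeat, which exaggerates regression to the mean. A simulation of 2,000,000 draws per setting added between-subject SD. It assumed no drug effect and repeats above 140 or below 90.

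| Mean (mmHg) | Between/within SD | Average fall after a reading > 140 | Repeat ≤ 140 | Repeat higher than trigger | Averaged shift |
|---|---|---|---|---|---|
| 115 | 8/5, 10/8 | 7.8, 11.6 | 76%, 74% | 12%, 13% | 0.0, 0.0 |
| 125 | 8/5, 10/8 | 5.4, 8.3 | 58%, 58% | 21%, 21% | −0.3, −1.0 |
| 135 | 8/5, 10/8 | 3.1, 5.3 | 35%, 39% | 32%, 31% | −0.9, −1.9 |

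Movement towards normal is a tendency. In 12% to 32% of cases the repeat is higher, and the rule then carries the more extreme value.

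**5. The ECG comparison.** The assignment rule is the same for both: an unscheduled value goes to the preceding scheduled time. ECGs are withheld only from a statistical analysis of intervals. Vital signs have no statistical analysis from which to withhold them, so the two policies do not conflict.

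**The case for a change.** The best case for a change is that SAP 7 states a general rule and SAP 7.8.3 a specific one. The specific one does not say that a superseded reading keeps its own row, actual time or difference. Laboratory and ECG listings carry flags for notable values, and SAP 7.8.3 specifies none for vital signs. The AE route rests on an investigator who knows the treatment (Protocol 4.1.5.1). With 6 active and 2 placebo subjects, each entry is read individually, so one displaced reading can matter to a reader. After 4 h the scheduled gaps widen to 2 h and more, so a late repeat can carry an early label.

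Part of this stands. SAP 7.8.3 leaves the row layout unstated, and a triggered entry would on average move towards normal. But SAP 7 calls for individual values, and a programmer following it would keep the superseded reading in the listing. Such a reader would then see both values and could take either difference by hand. The averaged shifts in the tables describe a mean change that the SAP does not produce. The SAP also does not say that repeats follow only abnormal readings; it offers follow-up or confirmation as an example. If summary tables of vital signs were ever reinstated, the choice would deserve another look.

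**Conclusion.** No change is needed. The two rules do combine so that a repeat supersedes the scheduled reading as the basis of the listed change. The consequence is confined to single entries in an eight-subject listing. In the first 4 h these would typically move by about 3 to 12 mmHg under the assumed blood-pressure values, sometimes in the other direction. No summary is biased because none is planned, the primary endpoint does not use the rule, and no dose escalation remains to be informed by it. Scheduled value and last value are both common conventions, and the plan applies last value to baseline and post-dose times alike.

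This conclusion rests on two readings: that SAP 7's commitment to list individual values covers superseded vital signs, and that vital signs stay listings-only as SAP 4 states. On that footing, the choice decides only which row shows a subtraction. Analysts can keep every reading visible with its actual time without any amendment to the SAP.

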7.8.4 ECG

Continuous safety ECG monitoring:

ECG recordings will be checked by the investigator for pathological results. Clinically relevant abnormal findings for ECG will be listed under 'Relevant Medical History / Baseline Conditions' (if they pre-exist prior to trial inclusion) or will be reported as AEs (if they occurred on treatment), and will be analysed as such. No separate ECG monitoring listing will be provided.

12-lead ECG:

Abnormal findings will be reported as baseline conditions (at screening) or as AEs (during the trial) if judged clinically relevant by the investigator, and will be analysed as such.

Additionally, a dataset of quantitative and categorical ECG endpoints will be provided to [REDACTED] for analysis by an ECG programmer at BI.

Listings of individual data of ECG endpoints will be shown in Appendix 16.2. Occurrences of notable findings will be flagged. Comments regarding the ECGs will be listed.

7.8.5 Others

Physical examination

Physical examination findings will be reported as relevant medical history/baseline condition (i.e., a condition already existent before intake of study drug) or as AE (if they occurred on treatment) and will be summarised as such. No separate listing or analysis of physical examination findings will be prepared.

10. HISTORY TABLE

Table 10: 1 History table

Version	Date (DD-MMM- YY)	Author	Sections changed	Brief description of change
1	12-FEB-2021	[REDACTED]	None	This is the final TSAP
